## 10.6 Sensitivity analyses

A per-protocol analysis will be carried out, restricted to participants who (a) attended  $\geq 6$  of the CMT sessions (applied to intervention arm only) and (b) did not undergo knee replacement prior to the 12-month outcome assessment (applied to participants in both arms). This analysis will address the efficacy of the CMT intervention under ideal adherence conditions.

A complete-case analysis will be performed, including only participants with complete outcome data at baseline and follow-up. This will provide a sensitivity check for the assumptions about missing data inherent in the base-case analysis.

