## 6.5 Treatment log

The physiotherapist will record the date and length of each of each treatment sessions for every participant in the CMT arm. These data will be transferred from the treatment log to the secure trial database by the trial manager (or another member of the team who is not blinded to group allocation) to provide a measure of attendance (date of first intervention session, date of final intervention session and total number of sessions attended). In addition, the following data will be recorded during the CMT treatment by the treating physiotherapist:

*Table 1: Treatment log*

	Time point	Description	Collected by
Clinical notes	After each clinical session	A pro forma will be used to summarise clinical presentation and capacity to engage with intervention techniques	Physiotherapist
Participant engagement score	At start of clinical sessions 2-7	
The physiotherapist will assess:
 
 
1. Engagement with the online learning platform
 
2. Written reflections on home practice (patient summary sheet)
 
3. Competence and understanding of previous week's challenges (home practice)
 
 
Based on this assessment, the physiotherapist will determine a weekly engagement score:
 
 
1. 0 = not engaged
 
2. 1 = low engagement
 
	physiotherapist

		3. 2 = full engagement	
--	--	------------------------	--

The weekly engagement score will be recorded in the clinical notes but will not be used as part of any analysis of trial outcomes. If scores are consistently below 2 then the physiotherapist will spend time at the end of each clinical session discussing barriers to engagement and creating an action plan with the participant to improve engagement and home practice.

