## 6.7 Potential for contamination

CMT is not currently available on the NHS and is only delivered through research studies which are being run by the University of Salford. Therefore, at present, it is not possible for patients outside this trial to access this treatment. However, this situation may change during the trial as we may offer training in CMT to private physiotherapists. In this situation, participants in the control arm could potentially access CMT through private providers, resulting in contamination. To mitigate against this, we have omitted the name of the CMT intervention from the participant information sheet. We will also collect information on physiotherapy accessed during the trial through the healthcare resource questionnaire (see 'Healthcare resource use questions').

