Following randomisation, the intervention coordinator (member of the research team) will liaise with participants in the intervention arm to schedule the intervention sessions. Once scheduled, participants will be sent a participant appointment information letter and schedule (see 'Group 1 Participant appointment letter'). Participants in the control arm will be sent the group 2 allocation letter (see 'Group 2 Allocation letter'). In some cases, research sites may use their own processes for booking and scheduling appointment. In this scenario, participants in the control arm will still be sent the same letter, however, participants in the CMT arm may receive the same information from their trust in a different format.

During the CMT treatment, the treating physiotherapists will keep a log of the number and length of appointments attended and will also record a weekly engagement score, as described in Section 6.5. Only attendance data will be used in the final analysis, with attendance of 6 (out of 7) sessions defined as achieving minimum adherence.

In some cases, it may be necessary to delay the collection of baseline data for up to 2 months from the point of consent. This may be necessary to facilitate scheduling of physiotherapy appointments for participants allocated to the CMT arm at research sites where there is limited capacity (due to physiotherapist availability) to deliver the intervention.

Table 2: Schedule of assessments

Assessment	Timepoint						
	Screening	Consent	Baseline	Intervention delivery (0-6 months)	6 months	12 months	13-14 months
Eligibility assessment	x						
Participant invitation	x						
Screening data	x						
Informed consent		x					
Data access form		x					
Baseline data and diversity and inclusion survey			x				
WOMAC			x		x	x	
GAKS					x	x	
PCS			x		x	x	
PSEQ			x		x	x	
WPAI-OA			x		x	x	
EQ-5D-5L			x		x	x	
Healthcare resource utilization			x		x	x	
Baseline qualitative survey			x				
Randomisation				x			
Physiotherapy sessions (CMT arm)				x			
Treatment log				x			
Adverse events				x	x		
Death				x	x	x	
Semi-structured interviews							x

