### 10.4 Primary outcome analysis

*Population:* All participants

*Treatments:* CMT + Usual care vs usual care alone , regardless of non-adherence or receipt of surgery to treat knee OA.

*Primary outcome:* Mean difference in WOMAC composite score at 12-month follow-up

*Handling of intercurrent events*

- Failure to complete CMT (attending fewer than 6 out of 7 sessions) – Treatment policy strategy
- Surgery to treat knee OA – Treatment policy strategy

The primary analysis will adopt a treatment policy strategy in line with the ICH E9(R1) estimand framework. All intercurrent events occurring after randomisation, including failure to complete the CMT intervention

(attending fewer than 6 out of 7 sessions) or undergoing knee surgery, will be considered part of the treatment effect. Participants will be analysed in the arm to which they were randomised regardless of these events. The primary outcome will be the adjusted mean difference in WOMAC composite score at 12 months: this will be estimated using a linear multilevel analysis of covariance (ANCOVA) model, including treatment arm (fixed effect), baseline WOMAC as a covariate, and site and receipt of surgery as random effects. The estimate of the difference for the WOMAC composite score between intervention arms will be presented with 95% confidence intervals and p-values: statistical tests will be two-sided. Missing primary outcome data will be replaced using multiple imputation under missing-at-random assumptions, and analyses will be conducted using the Stata MI command.

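### The per-protocol contrast in Section 10.6 is no longer randomised, so it does not show efficacy under ideal adherence without assumptions that the protocol does not state

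*Protocol*

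**What the plan says.** Protocol Section 10.6 lists a per-protocol analysis among the sensitivity analyses, with two rules. Rule (a) keeps those who attended at least six "of the CMT sessions (applied to intervention arm only"). Rule (b) keeps those who "did not undergo knee replacement prior to the 12-month outcome assessment (applied to participants in both arms"). The stated purpose follows: "This analysis will address the efficacy of the CMT intervention under ideal adherence conditions". No adjustment or weighting for these exclusions is described.

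Other sections bear on this:

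- Section 10.4: "The primary analysis will adopt a treatment policy strategy in line with the ICH E9(R1) estimand framework". This covers both non-completion of CMT and surgery.
- Section 8.7: "Only attendance data will be used in the final analysis, with attendance of 6 (out of 7) sessions defined as achieving minimum adherence".
- Section 6.5: the trial database will hold, for the CMT arm, "date of first intervention session, date of final intervention session and total number of sessions attended".
- Section 8.10: people who stop CMT may stay in follow-up. Section 8.9 foresees attendance ranging from four or fewer sessions to all seven.
- Section 6.7: at present "it is not possible for patients outside this trial to access this treatment". It adds that this may change, in which case "participants in the control arm could potentially access CMT through private providers, resulting in contamination".

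**The concern.** Rule (a) compares CMT participants who proved to be good attenders with all controls, including those who would have attended poorly if offered CMT. Attendance may go with motivation, general health or prognosis, and randomisation no longer balances these.

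Rule (b) selects on an event that CMT might change. Sections 8.7 and 10.9 plan further work if knee-replacement rates differ between the arms. Removing these patients from both arms looks even-handed, but the patients removed need not be alike in the two arms.

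At stake is how the result is read. A contrast that can show a benefit when there is none would carry an efficacy label fixed in the protocol. It also answers a different question from the treatment-policy estimand, so it does not test the robustness of the primary result.

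**Working it through.** **Inputs from the protocol (Section 10.1).** Baseline WOMAC mean 41.3, SD 17.8; 20% difference; effect size 0.46; 101 per group; 20% attrition.

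**The plan's own figures.** 0.20 × 41.3 = 8.26, stated as 8.3. 8.3/17.8 = 0.466 and 8.26/17.8 = 0.464, stated as 0.46. A two-sample t-test at effect size 0.46, two-sided 5% and 90% power needs 100.3, so 101 per group. 101/0.80 = 126.25, stated as 126. These reproduce and serve below only as a scale.

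**Assumptions, not in the protocol.** p = proportion of the CMT arm attending at least six sessions, 0.9 to 0.6. g = points by which non-attenders' 12-month WOMAC would be worse without treatment, 3 to 8. Surgery is left out at first.

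**Step 1: no true effect.** Let attenders' mean be m. The per-protocol CMT mean is m. The control mean is p × m + (1 − p) × (m + g) = m + (1 − p) × g. The difference is −(1 − p) × g, a false benefit.

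| p | g = 3 | g = 5 | g = 8 | Two-sided type I error, g = 8 |
|---|---|---|---|---|
| 0.9 | 0.3 | 0.5 | 0.8 | 6% |
| 0.8 | 0.6 | 1.0 | 1.6 | 9% |
| 0.7 | 0.9 | 1.5 | 2.4 | 14% |
| 0.6 | 1.2 | 2.0 | 3.2 | 20% |

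The range 0.3 to 3.2 is 4% to 39% of the 8.3-point target (0.3/8.3 and 3.2/8.3). The type I error uses SE = 17.8 × √(1/101 + 1/(101p)). At p = 0.8, SE = 2.66 and 1.6/2.66 = 0.60, so the error is 1 − Φ(1.96 − 0.60) + Φ(−1.96 − 0.60) = 0.09.

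A simulation (400,000 per scenario, ANCOVA on baseline, assumed correlation 0.5) gives per-protocol estimates of −0.8, −1.6, −2.4 and −3.3 for g = 8. The randomised estimate divided by p (the CACE) lies between −0.2 and 0. With g = 0 and no surgery, the per-protocol estimate is also about 0.

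**Step 2: true effect −8.3 in attenders, none below six sessions, p = 0.8, g = 8.** Intention-to-treat: 0.8 × −8.3 = −6.64. CACE: −6.64/0.8 = −8.3. Per-protocol: −8.3 − 1.6 = −9.9.

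**Step 3: where the CACE fails.** Suppose those below six sessions get half the benefit (−4.15).

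- p = 0.8: (0.8 × −8.3 + 0.2 × −4.15)/0.8 = −7.47/0.8 = −9.3.
- p = 0.7: (0.7 × −8.3 + 0.3 × −4.15)/0.7 = −7.06/0.7 = −10.1.

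The CACE then overshoots by 1.0 and 1.8 points.

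**Step 4: surgery.** Assume surgery in 10% of controls and 5% of the CMT arm, a 20-point gain from surgery, and p = 0.8, g = 8, effect −8.3 as in step 2. Intention-to-treat is −6.64 + 0.05 × 20 = −5.64, so the CACE is −5.64/0.8, about −7.0, because it includes the surgery effect. The simulated per-protocol estimate is −9.1. They miss −8.3 in opposite directions.

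**Step 5: precision.** The unadjusted intention-to-treat SE is 17.8 × √(2/101) = 2.50. At p = 0.8 the CACE SE is 2.50/0.8 = 3.13, against 2.66 for per-protocol. The 95% half-widths are about 6.1 and 5.2 points.

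**The case against.** The strongest reply has four parts.

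**The primary result is safe.** Primary and secondary analyses follow treatment policy, and the per-protocol result appears only as a sensitivity analysis. This stands. A reader might infer that the trial's conclusion is at risk, or that this figure will be the one quoted for completers; the protocol supports neither.

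**The bias is assumed.** The protocol gives no attendance rate, prognosis gap or direction. Eligibility requires being able to attend seven sessions and scheduling is flexible, so attendance may be high: at p = 0.9 the bias is only 0.3 to 0.8 points. If some people stop because they have improved, it reverses. The simulated gap was independent of baseline WOMAC; if baseline carried part of it, ANCOVA would remove that part. All this stands. It limits the size of the bias but does not justify an unqualified efficacy claim.

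**The CACE is no cure-all.** A reader might infer that per-protocol cannot show efficacy and that a CACE answers the same question from the same data. Neither follows. Per-protocol is unbiased if attendance and surgery are unrelated to prognosis given covariates. The CACE gives the effect in compliers rather than in everyone under ideal adherence, needs the exclusion restriction, and does not address the no-knee-replacement question. Nor does Section 6.7 rule out CMT use by controls, since it foresees private access.

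**This belongs in the SAP.** The absence of a CACE would not by itself be a finding, as no SAP is at hand. But Section 10.6 fixes both the exclusion rules and the interpretation, and these can be judged as written.

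**Conclusion.** The point holds in limited form. The per-protocol contrast in Section 10.6 is not a randomised comparison, and the efficacy sentence claims more than it delivers without assumptions that the protocol neither states nor supports. Under the assumed ranges, rule (a) alone produces a false benefit of about 0.3 to 3.2 points if non-attenders have the worse prognosis. The bias is nil if attendance is unrelated to prognosis, and it reverses if non-attenders do better. Rule (b) adds a bias of unknown direction. Because both exclusions change the question, the analysis is supplementary to the treatment-policy estimand rather than a sensitivity analysis of it. The documents support adding a CACE and relabelling the per-protocol result. They do not support outright replacement on the ground that the two answer the same question.

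**What to change.** 1. Pre-specify a supplementary CACE for 12-month WOMAC: two-stage least squares with randomised arm as instrument and baseline WOMAC and site as covariates, run within the multiple imputation. Leave out the receipt-of-surgery term of Section 10.4, which conditions on an event after randomisation.
2. Show it for at least six sessions and also for number of sessions or any session, because partial attendance may help (step 3). State the exclusion restriction.
3. Make private CMT use by controls identifiable. Section 6.7 relies on a questionnaire about physiotherapy in general.
4. State that the CACE is the effect in compliers with surgery handled as treatment policy, and that the effect without knee replacement is a separate hypothetical estimand. Reconcile the surgery wording of Section 10.4 with the knee-replacement wording of Section 10.6.
5. If the per-protocol analysis is kept, label it descriptive and supplementary, and delete or qualify the efficacy sentence.

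**Cost.** Attendance, allocation and outcome are already collected. The change needs a short analysis specification, some care in combining it with the imputation, and possibly one questionnaire item. The downside is a wider interval (about 6.1 against 5.2 points either side at p = 0.8) and dependence on the exclusion restriction.

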## 10.7 Interim analysis and criteria for the premature termination of the trial

The Sponsor may suspend or prematurely terminate either the entire study, or the study at an individual site, for significant reasons that must be documented (e.g. an unacceptable risk to participants or serious repeated

deviations from the protocol/ regulations). If this occurs the Sponsor shall justify its decision in writing and will promptly inform any relevant parties (i.e. participants, investigators, participating sites, REC, regulatory bodies).

No interim analyses of the outcome data will be undertaken before the final data is collected. However, the TMG/TSC will regularly review recruitment targets at each site. If recruitment is lower than anticipated, at any sites, then additional PICs will be identified, and the number of research sites may be increased.

## 10.8 Procedure(s) to account for missing or spurious data

Follow-up reminders and phone calls will be undertaken to minimise the missing outcomes, as described earlier in the protocol. For participants who complete outcomes electronically (using the trial database), there will be no missing data as it is not possible to submit partially completed questionnaires. For participants who complete paper outcomes, missing primary outcome data will be replaced using multiple imputation under missing-at-random assumptions, and analyses will be conducted using the Stata MI command.

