### Follow-up:

Following treatment, participants in the CMT arm will be sent an information letter/email explaining next steps of the trial (see 'Group 1 follow up information letter'). Participants in the control arm will also be sent an information letter (see 'Group 2 follow up information letter'). These letters/emails will inform participants of the dates that the follow-up questionnaire will be sent out.

At the two follow-up points, participants will receive a letter/email inviting them to complete outcome data (see 'Six-month questionnaire cover letter' and 'Twelve-month questionnaire cover letter'). For participants who opt to complete outcomes electronically, this letter will be sent via REDCap and contain a link to the online survey to complete outcomes. For those who opt for paper-based outcomes, this letter will be posted with the booklet of questionnaires.

A member of the research team who is blinded to treatment allocation will monitor return of all outcome data. This monitoring will allow the research team to identify missing outcome data and send reminders as appropriate. Reminders for the 6-month and 12-month outcome data will follow the schedule below:

- **At 3 days after the initial invitation to complete outcomes is sent**, if outcome data not completed, a Trial Administrator (or the REDCap system) will e-mail the participant with a reminder to complete outcomes (see 'Six-month questionnaire reminder letter' and 'Twelve-month questionnaire reminder letter').
- **At 1 week after the initial invitation to complete outcomes is sent**, if outcome data not completed, a Trial Administrator (or the REDCap system) will e-mail the participant again with a reminder to complete outcomes.
- **At 2 weeks after the initial invitation to complete outcomes is sent**, if outcome data not completed, a Trial Administrator (or the REDCap system) will e-mail the participant again with a reminder to complete outcomes. A text message will also be sent to the participant, and they will receive a follow-up call from a trial administrator.
- **At 3 weeks after the initial invitation to complete outcomes is sent**, if outcome data not completed, a trial administrator (blinded to group allocation), will telephone the participant to obtain a minimal data set. This minimal dataset will include the WOMAC questionnaire, the GAKS, and the EQ-5D-5L.

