# 10 STATISTICS AND DATA ANALYSIS

## 10.1 Sample size calculation and attrition

The minimally clinically importance difference in the primary outcome, the composite WOMAC score is 17-22% [38]. This trial is therefore powered to detect a 20% difference between groups in the composite WOMAC score at the primary end point (12 months). In our feasibility study, the baseline mean (SD) of the composite WOMAC score was 41.3 (17.8). A 20% change therefore equates to a change of 8.3 points, which gives an effect size of 0.46. Based on these estimates, 101 participants per group obtains 90% power for a two-sided test with type 1 error ( $\alpha$ ) set at 5%. Accounting for 20% attrition indicates a target of 126 participants per group.

We have mapped specific initiatives to reduce attrition. These include financial incentives, regular communication to participants through a newsletter and creation of a dedicated outcome data collection reminder schedule. With these additional measures, we are confident we can achieve an attrition rate less than 20%.

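### Sections 10.4 and 10.8 conflict on whose missing 12-month WOMAC is imputed, the 10.6 complete-case check does not test missing at random, and the telephone dataset omits surgery status

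*Protocol*

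**What the plan says.** - **Section 10.4** defines the primary analysis in all participants, as randomised, under a treatment policy strategy. On missing data: "Missing primary outcome data will be replaced using multiple imputation under missing-at-random assumptions, and analyses will be conducted using the Stata MI command". It makes no distinction by completion route. Its model includes receipt of surgery as a random effect.
- **Section 10.8** says that for participants who complete electronically "there will be no missing data as it is not possible to submit partially completed questionnaires". It continues: "For participants who complete paper outcomes, missing primary outcome data will be replaced using multiple imputation under missing-at-random assumptions".
- **Section 10.1** plans for loss: "Accounting for 20% attrition indicates a target of 126 participants per group". Section 8.5 foresees electronic users who do not answer reminders, Section 8.8 records uncollected outcomes as lost to follow-up, and Section 8.10 allows complete withdrawal with no further contact. None of these depends on the route.
- **Section 10.6** plans a complete-case analysis and says of it: "This will provide a sensitivity check for the assumptions about missing data inherent in the base-case analysis". It also plans a per-protocol analysis that excludes participants who had a knee replacement before the 12-month assessment.
- **Section 8.8** describes the telephone call made three weeks after the invitation: "This minimal dataset will include the WOMAC questionnaire, the GAKS, and the EQ-5D-5L". Surgery is recorded in the healthcare resource questionnaire (Section 3.3), which is not part of that call.

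**The concern.** Section 10.8 treats missing data as if it meant only skipped items. A form that cannot be submitted half-finished can still go unreturned, and its owner can withdraw. The section then states imputation for one group only, so two sections of one protocol give different rules for who is imputed in the primary analysis. That choice should not still be open once data have been seen.

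The second problem is what 10.6 says the complete-case analysis shows. Participants know their allocation and report the outcome themselves, so dropout related to how well they are doing is a serious risk. If the planned check shares the assumption that it is meant to test, agreement would be read as reassurance that it cannot give.

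The third is a data gap. The telephone call secures the WOMAC but not surgery status, which the 10.4 model and the 10.6 exclusion both use. Analysis cannot recover an answer that was never collected.

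**Working it through.** **1. The planned number missing.** Inputs from Section 10.1: baseline mean 41.3, SD 17.8, 20% difference, 90% power, two-sided 5%, 20% attrition.
- Target difference: 0.20 × 41.3 = 8.26, stated as 8.3. Effect size: 8.26 / 17.8 = 0.46.
- An effect size of 0.46 needs 100 per group by the normal formula, or 100.3, so 101, by the t-based formula. This reproduces "101 participants per group obtains 90% power for a two-sided test with type 1 error".
- 101 / 0.80 = 126.25, stated as 126; 2 × 126 = 252.
- Expected missing: 0.20 × 252 = 50.4, about 50, or 25 per arm.

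**2. How many fall outside the 10.8 rule.** The electronic share is not given, so it is varied. Non-response is assumed equal on both routes.

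| Assumed electronic share | Outside the 10.8 rule | Outside the 10.4 rule |
|---|---|---|
| 30% | 50.4 × 0.3 = 15 | 0 |
| 50% | 50.4 × 0.5 = 25 | 0 |
| 70% | 50.4 × 0.7 = 35 | 0 |
| 90% | 50.4 × 0.9 = 45 | 0 |

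The boundary is itself unclear: someone on the paper route who returns nothing has not completed paper outcomes either.

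**3. Whether complete-case analysis can check the assumption.** Simulation of 400 trials of 126 per arm, each with 20 imputations. Assumptions: baseline and outcome SD 17.8, correlation 0.5, true difference -8.26, ANCOVA on baseline, no auxiliary variables, no site or surgery term. Control outcomes are missing at random at 20%. In the CMT arm, worse scores are more likely to be missing (log-odds rise by 1 per 10 points). Missingness came to about 24% in the CMT arm and 20% in control.

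| Analysis | Mean estimated difference |
|---|---|
| Full data | -8.28 |
| Complete-case ANCOVA | -12.22 |
| Multiple imputation under missing at random | -12.23 |

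Both analyses are off by about 4 points (12.22 - 8.28 = 3.94), yet differ from each other by only 0.18 points on average within a trial. The mechanism is strong on purpose: 3.94 / 0.24 is about 16 points of departure among the missing, close to one SD. It shows that the two methods move together; it is not a forecast of bias.

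**4. Size of a departure from missing at random.** If the missing CMT participants are worse than predicted by δ, the arm difference shifts by 0.20 × δ:
- δ = 4: 0.8 points
- δ = 8.3: 1.7 points
- δ = 12: 2.4 points

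**5. Other sources of surgery status.** The resource questionnaire covers 6 and 12 months (Section 3.3) but is not in the telephone dataset. Elective or pre-planned treatment is exempt from SAE reporting and left to the participant questionnaires (Section 9.1.2). Event recording ends at six months (Section 9.2.1). Registry follow-up depends on further funding (Sections 8.7 and 10.9). For someone who returned the 6-month questionnaire and was reached only by telephone at 12 months, surgery in months 6 to 12 has no other stated source.

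**The case against.** **Section 10.4 already covers attrition.** This stands. The section that defines the primary analysis imputes every missing primary outcome. A reader of 10.8 alone might infer that electronic non-responders are dropped from the primary analysis, or that most of the 20% attrition goes unhandled. The protocol does not support either reading: the first lets 10.8 override 10.4, and the second needs an electronic share that is not given. What remains is a contradiction.

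**Section 10.8 may mean only item gaps in submitted forms.** This is a natural reading, since the preceding sentence plans reminders to reduce missing outcomes. But the sentence that limits imputation to paper completers would still differ from 10.4.

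**Imputation details and further sensitivity analyses may sit in a statistical analysis plan that is not shown.** This stands, so their absence is not the finding. The criticism is of what 10.6 claims for complete-case analysis. With auxiliary variables such as 6-month WOMAC in the imputation model, the two analyses would use different information and comparing them would tell more. It would still not test informative dropout.

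**The shifts in step 4 are modest.** At the planned effect this is true. With SE = 17.8 × √(2/101) = 2.50, a shift of 1.66 leaves 8.3 - 1.66 = 6.64, and 6.64 / 2.50 = 2.7. But the threshold for significance is 1.96 × 2.50 = 4.9, so an observed difference between 4.9 and 4.9 + 1.7 = 6.6 would lose significance under the same shift. This SE ignores any gain from baseline adjustment.

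**Surgery status is not wholly unknown for telephoned participants.** This stands: surgery up to month 6 may be known from the 6-month questionnaire. The gap is months 6 to 12.

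**Conclusion.** The concern holds as a conflict of rules, an overstated check and a data gap.

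- Sections 10.4 and 10.8 state different imputation rules for the primary outcome. On the 10.8 wording an unknown share of about 50 missing outcomes lies outside the rule: about 15 to 45 if 30% to 90% of participants use the electronic route and non-response is equal by route. Both conditions are assumptions.
- The complete-case analysis in 10.6 cannot do what that section says. When only the outcome is missing and no auxiliary variables are used, it relies on essentially the same assumption as the imputation, and the two agree even when both are wrong.
- Surgery in months 6 to 12 has no other stated source for participants reached only by telephone at 12 months, although 10.4 and 10.6 use it.

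The sample size is not affected. Section 10.9 refers to itself for the imputation method; that is a clerical slip, though if 10.8 is meant the economic analysis inherits the same ambiguity.

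**What to change.** 1. Align 10.8 with 10.4: multiple imputation covers every randomised participant with a missing 12-month WOMAC, whatever the completion route.
2. Limit the electronic statement in 10.8 to item-level gaps in submitted forms.
3. In 10.6, keep the complete-case analysis but supplement it with delta-adjusted multiple imputation, with delta varied separately by arm. Drop the claim that the complete-case analysis checks the missing-data assumptions.
4. Add one knee-surgery question (yes/no, date) to the telephone minimum dataset before follow-up calls begin.
5. Correct the cross-reference in 10.9.

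Cost: protocol wording, a few lines of analysis code and a slightly longer call. No change to the sample size.
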